### 1.2.4 Justification for choice of intervention

IUI is a simpler, cheaper, and less invasive alternative treatment to IVF. Studies have shown that IUI can offer a similar likelihood of successful pregnancy as IVF (25, 26). Further studies have suggested that it requires three cycles of IUI in order to achieve pregnancy rates similar to those of one cycle of IVF (8). Supporting this clinical justification, the patient perspective highlights that there is a strong desire for interventions that are less invasive, less expensive, require fewer hospital visits, and yet retain an acceptable outcome success rate. The choice of IUI is also notable as something offered broadly in an unlimited fashion across Belgian fertility centres on the basis of financial modelling (27). Partners providing eggs in couples randomised to the IUI arm of the study will undergo ovarian

stimulation using letrozole as it is likely that these achieve a slightly higher live birth rate than clomid (28-30).

A subsequent cycle of IVF after three cycles of IUI will be offered to couples. Though this cycle is not part of the trial intervention, information on the outcome of these cycles will be collected. Consideration has been given as to whether it is an appropriate comparison when in one arm the IVF cycle occurs immediately and in the other it will be delayed by many months due to the IUI ovarian stimulation. This will be considered when interpreting the outcomes, but any detectable effect would only occur in the oldest eligible patients, and it was determined not appropriate or acceptable to delay direct IVF entry to those in that trial arm. This is because published HFEA data reflects rapid decreases in IVF success as the partner providing eggs age goes beyond 38 (1) – as such providing these patients a non-treatment trial delay would significantly decrease their chance of a child and be unethical.

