# 2.2. Main trial objectives

### 2.2.1. Clinical aims and objectives

The primary objective is to test the hypothesis that in couples with UEI, the policy of offering three cycles of IUI is not substantially worse than the policy of offering IVF by up to a 10% margin of non-inferiority in terms of live birth \ge 34 weeks [MRC/NIHR framework, core element 4: uncertainties].

The secondary clinical objectives for the trial are:

- 1. To evaluate the rates of pregnancy loss for IUI versus IVF for couples with UEI.
- 2. To compare the health of babies born as a result of IUI versus IVF to couples with UEI.
- 3. To compare the complication rates of the two treatment arms.
- 4. To evaluate the TTP leading to a live birth for IUI versus IVF for couples with UEI.
- 5. To explore patient satisfaction in the two treatment arms.
- 6. To compare outcomes of couples over a longer period of 25 months post-randomisation when further interventions may have been provided.
- 7. To explore the different clinical features of IUI and IVF cycles.
- 8. To explore the reasons patients may not complete the full course of treatment or wish for different treatment options.

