### 8.2.2. Secondary outcomes

#### 8.2.2.1. Clinical

#### **Pregnancy outcomes**

The following outcomes will be assessed at two time points: 19 months post-randomisation to allow for pregnancy outcomes to be obtained and concern pregnancies conceived within 270 days (approximately 9 months) of randomisation; and 25 months post-randomisation to allow for pregnancy outcomes to be obtained and concern pregnancies conceived within 450 days (approximately 15 months) of randomisation. This will enable us to determine the medium-term effect of the initial treatment policy decision.

- Singleton live birth ≥37 weeks;
- TTP leading to a live birth defined as time from randomisation to pregnancy in days (censored at 270 days);
- Cycle cancellation and reason (failure to respond / over-response);
- Biochemical pregnancy;
- Clinical pregnancy;
- Ongoing pregnancy at 12 weeks (range 11 to 14 weeks);
- Multiple pregnancy;
- Ectopic pregnancy;
- Miscarriage (defined as delivery before 24 weeks of gestation);
- Stillbirth (defined as intrauterine death ≥24 weeks);
- Termination:
- Number of embryos remaining (IVF group).

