## **Complications**

The following outcomes will be assessed:

i.) for the first IVF treatment within 450 days post randomisation for a period of 60 days following the date of FSH injection;

- ii.) for the first three IUI cycles within 450 days post randomisation for a period of 30 days following the date of ovarian stimulation for partial or cancelled cycles, or date of insemination for complete cycles.
  - Ovarian hyperstimulation syndrome (mild, moderate, severe);
  - Pelvic infection;
  - Bleeding post oocyte retrieval (IVF only);
  - o Admission to High Dependency Unit (HDU)/ Intensive Therapy Unit (ITU), standard ward admission, A&E visit or Outpatient review.

The following outcomes will be assessed at 28 days post birth (or patient's discharge date from hospital whichever is sooner).

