### 14.2.2. Secondary outcomes

The secondary outcomes that are binary (i.e., yes/no) will be analysed using the same methods as described for the primary outcome (see Section 14.2.1), with corresponding 95% confidence intervals (this includes the longer-term assessment at 25 months). For those secondary outcomes that are continuous (e.g. Gestational age at delivery, Birthweight, CSQ-8 score), mixed effects linear regression methods will be utilised to calculate an adjusted mean difference and 95% confidence interval. Time-to-event outcomes (e.g. TTP leading to a live birth) will be analysed using a mixed effects ('frailty') Cox Proportional Hazard model, allowing the same minimisation variables as fixed effects and randomising centre as a random effect. The treatment effect will be expressed as adjusted hazard ratio with 95% confidence interval. Regarding safety, the total number of participants experiencing SAEs will be given by allocation group along with a descriptive table of the events, and statistical significance will be determined by a chi-square test; other safety data including complications will be tabulated by group but are not expected to be formally analysed.

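### Peri-treatment complications have a 450-day horizon only, so the by-arm table mixes follow-on IVF into the IUI column and gives no safety result to match the 270-day primary outcome

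*Protocol*

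**What the plan says.** **Complications (Section 8.2.2.1).** The peri-treatment items are defined by type of treatment, not by arm: "for the first IVF treatment within 450 days post randomisation for a period of 60 days following the date of FSH injection" and "for the first three IUI cycles within 450 days post randomisation for a period of 30 days following the date of ovarian stimulation" (or of insemination, for complete cycles). No 270-day version is given.

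**Pregnancy and birth outcomes (same section).** These have two horizons: "The following outcomes will be assessed at two time points: 19 months post-randomisation", which "concern pregnancies conceived within 270 days (approximately 9 months) of randomisation", and 25 months, which "concern pregnancies conceived within 450 days (approximately 15 months) of randomisation". The primary outcome (Section 8.2.1) uses the 270-day limit.

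**Follow-on IVF.** Section 1.1.4 expects every couple unsuccessful after three IUI cycles to go on to IVF. Section 7.1.1 offers it as clinical care, outside the trial intervention. Section 1.2.4 (choice of intervention) says: "Though this cycle is not part of the trial intervention, information on the outcome of these cycles will be collected". The notes to the schedule of assessments (Section 9.1) bar it in the IUI arm before day 270.

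**Objective and presentation.** Secondary objective 3 is "To compare the complication rates of the two treatment arms". Section 14.2 analyses all outcomes by randomised group, and Section 14.2.2 says that "other safety data including complications will be tabulated by group but are not expected to be formally analysed".

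**The concern.** Lower risk is one of the reasons Section 1.1.4 gives for interest in IUI, and secondary objective 3 is meant to examine it. Followed as written, the plan compares up to three IUI cycles plus one IVF cycle in the IUI arm with one IVF cycle in the IVF arm. Bleeding after egg collection, which only IVF can cause, could appear in the IUI column.

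This has two consequences. First, the 270-day efficacy result has no safety result on the same footing, so benefit and harm of the allocated treatments cannot be read side by side from the specified tables. Secondly, the 450-day count is uneven as a policy comparison. It takes in the IUI arm's follow-on IVF because that is the couple's first IVF, but it leaves out any second IVF in the IVF arm, which Section 1.1.4 recognises may happen where funding allows.

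The concern is the horizon and the pooling, not the 30-day and 60-day windows after each cycle.

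**Working it through.** **1. The plan's own figures.** The protocol gives no complication rates, so the figures to reproduce are the three-cycle IUI success rates in Section 14.1.
- At 6.4% per cycle: 1 − 0.936³ = 1 − 0.820 = 18.0%.
- At 10.36% per cycle: 1 − 0.8964³ = 1 − 0.720 = 28.0%.
- Cycles per couple: 1 + 0.936 + 0.936² = 2.81, and 1 + 0.8964 + 0.8964² = 2.70.

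These agree with the protocol's 18%, 28%, 281.2 and 270 (the last two per 100 couples).

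**2. Couples who could have follow-on IVF.** With 471 couples per arm:
- at 18% success, 82%, or 0.82 × 471 ≈ 386 couples;
- at 28% success, 72%, or 0.72 × 471 ≈ 339 couples.

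At those success rates this is an upper bound on IVF by day 450. Some couples will conceive naturally, be pregnant, decline, or start later.

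**3. Dilution.** Let v be the complication risk of an IVF cycle (taken as equal for first-line and follow-on IVF), u the risk per IUI cycle, k the IUI cycles per couple, and f the share of the IUI arm having IVF by day 450.
- Risk from IUI alone: c = 1 − (1 − u)^k
- Difference due to allocated treatment: v − c
- Difference in the by-arm table: v − [c + f·v·(1 − c)]

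If u is negligible, c = 0 and the by-arm table retains the fraction 1 − f of the true difference, whatever v is.

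| Uptake among unsuccessful couples (assumed) | f at 18% / 28% success | Share of difference shown |
|---|---|---|
| 100% | 0.82 / 0.72 | 18% / 28% |
| 75% | 0.615 / 0.54 | 39% / 46% |
| 50% | 0.41 / 0.36 | 59% / 64% |

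Example with v = 5% (assumed) and full uptake: IUI cycles alone 0%, pooled IUI column 4.1% or 3.6%, IVF column 5%.

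**4. If IUI is not negligible.** Take v = 5% and u = 0.5% per cycle (both assumed). IUI alone gives c = 1.40% or 1.34%, so the allocated-treatment difference is 3.60 or 3.66 points. At full uptake the pooled IUI column is 5.44% or 4.90%, leaving −0.44 or +0.10 points. At 50% uptake 1.58 or 1.88 points remain, which is 44% or 51%.

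**5. What a 270-day cut would isolate.** Section 7.1 has treatment in both arms start within three months of randomisation, and Section 9.1 places the three IUI cycles at roughly months 2 to 6. Most allocated treatment should therefore start before day 270, while the Section 9.1 note keeps follow-on IVF after it. The cut may not be perfectly clean, because the passages on timing differ. Section 7.1.1 offers IVF after three IUI cycles or at 270 days, and Section 15.2 speaks of eight months. These need reconciling. A split by treatment type works however that is settled.

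**The case against.** The strongest reply is that the 450-day by-arm count is the right one. The trial compares policies, analyses all outcomes by intention to treat, and has an objective on outcomes after further interventions. IVF complications after failed IUI are part of what the IUI policy leads to, and Section 10.3 deliberately brings the first IVF cycle in the IUI arm into serious adverse event reporting. This stands: the table is legitimate as a policy comparison and should stay. The fault is that it is the only one specified, and that it counts repeat IVF unevenly.

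It can also be said that table layout belongs in the SAP, which is not at hand. That is fair for layout. The 450-day horizon, however, is set in the protocol's outcome definition, beside outcomes that were given two horizons.

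The consequence is limited as well. Complications are descriptive, secondary outcomes are exploratory, and the non-inferiority conclusion does not depend on them. Section 1.1.1 notes that England most often funds a single IVF attempt, so the omission of second cycles may be small.

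Three stronger readings are tempting, and the protocol does not support them.
- A reader might infer that the trial cannot show the complications of the allocated treatments. It can: the definition separates IVF from IUI, the treatment forms are type-specific, and CRFs repeat per cycle (Section 11.2). The protocol just does not call for the split.
- A reader might infer that counting stops at day 450. That day limits which treatments qualify; follow-up runs 30 or 60 days beyond, to about day 480 for IUI and day 510 for IVF. Antenatal, intrapartum, post-partum and neonatal complications have their own window after birth.
- A reader might infer that most of the risk difference is bound to disappear. That needs high uptake by day 450. At 50% uptake and negligible IUI risk, more than half remains.

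**Conclusion.** The point holds in a limited form. For the peri-treatment complications, the protocol fixes one horizon that takes in IVF outside the trial intervention, tabulates by randomised group, and offers nothing matching the 270-day primary outcome. Objective 3 would then be answered by a contrast diluted towards no difference between IVF and IUI, or even reversed if IUI cycles carry some risk of their own.

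With negligible IUI risk, the by-arm table would show between 18% to 28% of the allocated-treatment difference (full uptake) and 59% to 64% (50% uptake). The 72% to 82% share behind the first range follows from the protocol's success rates and is an upper bound at those rates. Uptake by day 450, the complication rates in the examples, and equal risk for first-line and follow-on IVF are assumptions. The effect of leaving out second IVF cycles cannot be sized from the protocol.

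This is a cheap improvement to the safety reporting. The primary analysis is unaffected.

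**What to change.** In Sections 8.2.2.1 and 14.2.2:

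1. Add a by-arm tabulation of the peri-treatment complications for treatment cycles started within 270 days of randomisation.
2. Keep the 450-day by-arm table as the policy comparison, and label it as covering the first IVF only.
3. In both tables, split IUI-arm events into those after IUI and those after follow-on IVF.

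The cost is a few lines of protocol and SAP wording and one more descriptive table, drawn from cycle dates and treatment types already on the CRFs. No new collection on repeat IVF or frozen transfers is needed; labelling the 450-day table deals with that gap openly. The extra table should stay descriptive, as Section 14.2.2 intends, because event numbers may be small.

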### **6.4.1.** Randomisation process

After eligibility has been confirmed, informed consent has been given and, if applicable, payment has been received, the participant can be randomised into the trial using the online system. All questions and data items on the online Randomisation Form must be answered prior to a potential participant being randomised into the trial. The couple should only be randomised if (in the opinion of the site PI) there is a high likelihood of treatment starting (defined as date of ovarian stimulation) within 3 months of randomisation in both groups.

Following randomisation, a confirmatory email will be sent to the research team at the relevant HFEA licenced fertility treatment centre and the UNITY Trial Office.

The couple do not need to be present for the randomisation process. In this case, it is the responsibility of the local research team to notify the couple of their allocation and how they proceed on that treatment pathway.

The local research team should add the participant to the UNiTY Participant Recruitment and Identification Log which links participants with their Couple Trial ID. PIs or their delegates must ensure this document is stored securely and it must not be submitted to the Trial Office. The UNiTY Participant Recruitment and Identification Log should be held in strict confidence.

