# Definition of cancelled and complete treatment cycles

- IVF and IUI cycle cancellation if the partner providing eggs has had a stimulation injection, but the rest of the procedure was cancelled prior to egg collection (IVF), or insemination (IUI).
- Complete cycles if embryo transfer (IVF) or insemination (IUI) has taken place.

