# Cancelled cycles and trial data

When cycles are cancelled it will be at the discretion and cost of the provider (treatment centre) as to whether a complimentary cycle is offered. Any replacement cycles will be recorded as non-trial treatments.

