#### 8.2. Main trial outcomes

#### 8.2.1. Primary outcome

The primary outcome is the live birth of a baby at ≥34 week's gestation, conceived within 270 days of randomisation (approximately 9 months). Date conceived is determined as date of egg collection for couples who have undergone fresh embryo IVF, date of embryo transfer minus the number of days of culture for couples who have undergone frozen embryo IVF, date of insemination for couples who have undergone IUI, and 14 days after the first day of the last period for couples who have conceived naturally.

In line with the evaluation of treatment policy, initial or subsequent pregnancies may be included within this timeframe. This outcome will be assessed at 19 months post-randomisation.

\_\_\_\_\_\_

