11.2. Case Report Form (CRF) completion

The CRFs will include (but will NOT be limited to) the Forms shown in **Error! Reference source not found.** 

**Table 6**: Case report forms in UNiTY

Form Name	Schedule for submission
Informed Consent Form (one for each partner)	Prior to randomisation
Screening CRF	Prior to randomisation
Baseline CRF	Prior to randomisation
Baseline participant questionnaire: - EQ-5D-5L	Prior to randomisation
Treatment CRFs: - IVF treatment CRF - IUI treatment CRF - Laboratory CRF - Frozen Transfer CRF	During or as soon as possible after treatment
Outcomes CRF: - Post-treatment CRF	8 weeks after treatment starts (defined as the first day of ovarian stimulation) in order to capture all potential complications/outcomes.
Outcomes CRF: - Clinical Pregnancy outcome CRF	As soon as possible after each follow up assessment time point (19 months and 25 months post randomisation)
Outcome participant questionnaires  - EQ-5D-5L (one questionnaire to be completed for each partner)  - CSQ-8 (one questionnaire to be completed for each partner)  - Health resource use (one questionnaire to be completed per couple)	As soon as possible after each follow up assessment time point (during the first treatment cycle of IUI and/or IVF, 19 months and 25 months post randomisation)
Non-trial treatment form	During or as soon as possible after treatment
Natural pregnancy notification CRF	As soon as possible after becoming aware of participant's pregnancy
Serious Adverse Event Form	If expedited: emailed within 24 hours of site research team becoming aware of event If non-expedited: emailed within 4 weeks of site research team becoming aware of event
Change of Status Form	As soon as possible after the point of reduced participation
Deviation Form	As soon as possible after a protocol deviation has occurred

A CRF should be completed for each couple or individual participant as documented at the top of each document. CRFs repeat to account for multiple treatment cycles and multiple pregnancies.

In all cases it remains the responsibility of the PI to ensure that the CRF has been completed correctly and that the data are accurate. This will be evidenced by the signature of the PI, or delegate(s). The Site Signature & Delegation Log will identify all those personnel with responsibilities for data collection.

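### The IVF complication outcome does not say how a cycle cancelled before egg collection is handled; as defined, it leaves out the replacement cycle, and its form falls due before the 60-day window closes

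*Protocol*

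**What the plan says.** Section 8.2.2.1 (Complications) sets two observation rules for treatment complications: OHSS, pelvic infection, bleeding after oocyte retrieval, and admissions or visits.

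- Item (i), IVF: "for the first IVF treatment within 450 days post randomisation for a period of 60 days following the date of FSH injection". Cancelled cycles are not mentioned.
- Item (ii), IUI: "for the first three IUI cycles within 450 days post randomisation for a period of 30 days following the date of ovarian stimulation" where the cycle is partial or cancelled, and 30 days from insemination where it is complete.

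Section 7.6 treats an IVF cycle as cancelled "if the partner providing eggs has had a stimulation injection, but the rest of the procedure was cancelled prior to egg collection (IVF"). It leaves any complimentary replacement to the provider's discretion and cost, and adds: "Any replacement cycles will be recorded as non-trial treatments".

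Section 10.3 limits SAE reporting to trial-related treatment, with one exception: the first IVF cycle in the IUI arm. SAEs from other non-trial treatment stay in the medical notes.

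For the primary outcome, section 8.2.1 says that "initial or subsequent pregnancies may be included within this timeframe". Table 9 includes conceptions after further IUI, IVF or frozen transfer in the primary intention-to-treat population of both groups.

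Table 2 names the Post-Treatment CRF as the form for complications. Its note X5 and Table 6 both time that form from the start of stimulation; Table 6 says "8 weeks after treatment starts (defined as the first day of ovarian stimulation) in order to capture all potential complications/outcomes".

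**The concern.** Comparing complication rates is secondary clinical objective 3 (section 2.2.1). Section 1.1.2 names OHSS as the main risk of IVF, and section 1.1.4 gives lower risk as part of the case for IUI. Section 14.2.2 says complications will be tabulated without formal analysis, so the outcome definition alone decides what a reader sees.

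Consider a couple whose IVF cycle is stimulated, cancelled before egg collection and then replaced. The replacement contains their only egg collection. If the 60-day window stays with the cancelled cycle, bleeding after retrieval cannot occur in the assessed treatment, and harms of the retrieval that did take place have no place in the outcome. Because replacement is discretionary, the extent of the gap would differ between sites. Because item (i) is silent, sites could also code the same situation differently.

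**Working it through.** No figure in the protocol is in dispute. The sample size supplies only the 471 couples per arm used below. It reproduces: (1.960 + 1.2816)² × 2 × 0.28 × 0.72 / 0.10² = 423.7, so 424 per arm and 848 in total; 848 / 0.90 = 942.2, against 942 stated. The check is mainly a reading of the definitions together.

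**Which cycle is the first IVF treatment?**

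1. Section 6.4.1 speaks of "treatment starting (defined as date of ovarian stimulation) within 3 months of randomisation in both groups". Note X5 and Table 6 use the same starting point.
2. By section 7.6, a cancelled IVF cycle has already had a stimulation injection. It has therefore started.
3. Item (i) counts its 60 days from the FSH injection, which the cancelled cycle has had.
4. The cancelled cycle is therefore the first IVF treatment, and the window belongs to it.

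**Where does the replacement cycle fall?**

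| Purpose | Cancelled first cycle | Replacement cycle |
|---|---|---|
| Complication outcome (8.2.2.1) | Included | Outside: not the first IVF treatment |
| Trial status (7.6) | Trial treatment | Non-trial |
| SAE reporting to the trial office (10.3) | Yes, if serious and related | No |
| Live birth of at least 34 weeks conceived by day 270 (8.2.1, Table 9) | Not applicable | Counts |

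The word *first* does more of the excluding than the non-trial label. The first IVF cycle after IUI is also outside the trial intervention (section 7.1.1), yet sections 8.2.2.1 and 10.3 both cover it.

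**How many couples?** The protocol gives neither the proportion of IVF cycles cancelled before egg collection (c) nor the proportion of those replaced (r). The number of IVF-arm couples with a replacement cycle is 471 × c × r. With assumed ranges of c = 2% to 15% and r = 25% to 100%:

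- lowest: 471 × 0.02 × 0.25 = 2.4 couples
- highest: 471 × 0.15 × 1.00 = 70.7 couples

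If those cycles succeeded at the protocol's 28% with conception by day 270, they would yield 2.4 × 0.28 = 0.7 to 70.7 × 0.28 = 19.8 primary-outcome births. So wide a range reflects the assumptions and is no estimate.

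**Form against window.** 8 weeks × 7 = 56 days, and 60 − 56 = 4 days. This takes the first FSH injection as the first day of stimulation. For a completed IUI cycle the 30-day window closes before the form is due provided insemination is within 56 − 30 = 26 days of starting stimulation, so the mismatch concerns IVF.

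**The case against.** The strongest reply is that the exclusion is inferred. No sentence says that a cancelled cycle uses up the first IVF treatment. That is correct. The FSH starting point and the definition of treatment start favour this reading, but the defect is best described as an undefined term whose most natural reading leaves a gap.

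A second reply is that a fixed first-course safety outcome beside a treatment-policy birth outcome is a legitimate design, and that replacement IUI cycles are also non-trial (a withheld insemination already counts as one of three attempts under section 7.3). This stands in part. It is why any fix should cover both treatments and keep the first-course comparison visible. It does not explain why item (i) is silent where item (ii) is explicit.

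Third, data may exist. There is a non-trial treatment form whose content is not shown, and CRFs repeat across cycles. If a replacement starts quickly, some events may also fall by date inside the first window. Both are possible, but the outcome definition neither uses such data nor says how to attribute them.

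A reader might also infer stronger conclusions that the document does not support:

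- *Couples cancelled for over-response are omitted.* They are not. Their FSH injection opens the window, so OHSS from the cancelled cycle is captured, and over-response cancellation is itself a secondary outcome.
- *The IVF complication rate is understated by a stated percentage.* Any such figure comes from assumed cancellation and replacement rates.
- *Days 57 to 60 are lost in every window.* For trial treatment, related SAEs are reportable until 60 days after the cycle outcome (section 10.3), and OHSS admissions are uploaded within four weeks of the event (section 10.4.2). Table 2 also marks complications at later months, although it names the same form as their source.

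**Conclusion.** The point holds as a gap in the outcome definition plus a scheduling mismatch. Followed as written, the complication table would omit treatment harms from some couples' only egg collection, while a qualifying birth from that cycle would count in the primary outcome. This rests on reading sections 6.4.1, 7.6, 8.2.2.1 and 10.3 together, since item (i) does not address cancelled IVF cycles.

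The size is unknown. Observing the replacement as well could only leave unchanged or raise the number of IVF-arm couples with a recorded treatment complication. Replacement IUI cycles are left unclear too, so the net effect on the comparison between arms cannot be stated. The consequence is limited: secondary outcomes are exploratory (section 14.2), complications are tabulated only, and antenatal, intrapartum, postpartum and neonatal complications carry no first-IVF restriction. The primary outcome, the margin and the non-inferiority decision are untouched.

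The form mismatch needs no assumed rates. Complications arising on days 57 to 60 of an IVF window can be missed if they are not otherwise reported as SAEs or OHSS admissions.

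**What to change.** 1. In section 8.2.2.1 item (i), state that cancelled IVF cycles are included. Collect complications for each IVF stimulation up to and including the first that reaches egg collection, replacements included, in both arms, for 60 days from each FSH start. Apply the corresponding rule to replacement IUI cycles under item (ii). Tabulate replacement-cycle complications separately, so that the first-course comparison stays visible and differences between sites in offering replacements do not blur it.
2. In section 7.6, add that replacement cycles remain subject to complication collection although they are recorded as non-trial treatment.
3. In Table 2 note X5 and in Table 6, schedule the IVF Post-Treatment CRF after day 60, for example at 9 weeks (63 days).

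The cost is an extra form for each couple with a replacement cycle and a delay of about a week to one existing form. Treatment, the primary outcome and the sample size do not change.
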